The mean outcome scores of the mHHS in each treatment group at 12 months will be compared to baseline scores to assess for significant differences using paired sample t-test in SPSS 16 (SPSS, Chicago, IL). The mean outcomes scores of the mHHS between groups at 12 months will be compared using independent t-tests to assess for significant difference. We will use a Levene test to judge variance and proceed accordingly. If a statistically significant difference is detected during these analyses, we will calculate the effect size (ES) to determine how meaningful these results are outside of being statistically significant. The ES will be calculated by: [(mean mHHS score of surgical arm / mean mHHS of the conservative group) / standard deviation of the conservative group]. According to Cohen ⁵⁸, an ES <0.1 is trivial, ES of 0.1-0.3 is minimal, ES of 0.3-0.5, is moderate, and ES >0.5 is large. We will repeat the same analysis at 12 months.

Hypothesis 2.1, 2.2, and 2.3:

Diagnosis and treatment of the prearthritic and early arthritic hip has been an area of intense interest. However, our most conventional method of assessment (plain radiography) does not provide us with enough diagnostic sensitivity.⁴¹ Direct visualization on the articular surfaces in the hip is both sensitive and specific. Furthermore, emphasis is being placed on the location of arthritis as a prognostic indicator of good outcomes following hip arthroscopy. The value of arthroscopic techniques for primary

symptoms and/or prevention of OA secondary to labral tears remains unclear even though preliminary reports indicate there may be some benefit to repairing a torn labrum, even in cases of severe OA. Evaluation of arthritic change at the time of arthroscopy is important, particularly in subjects where there remains uncertainty about the efficacy of labral repair for those with articular or rim cartilage degeneration that the effects of those changes on long-term OA progression.⁵⁹

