Using the data from our retrospective review of outcomes following labral repair, a 10 point or greater difference on the mHHS as significant, and a single-tail independent t-test to evaluate the difference between means with 80% power and a 5% significance level, 35 subjects are needed to demonstrate a statistically significant difference between the average mHHS of the conservative group and surgical group. Testing of hypothesis 1.5 will be an intragroup analysis looking for a significant difference in outcome measures from the time of completion of PT (non-crossover) when compared to the same data to be collected at 12 months and 24 months. The purpose is to determine the short-term durability of the response to PT, if one is found.

70 study completers should provide us with the necessary data needed to substantiate or reject our hypothesis. There has been no prospective trial to date testing these hypotheses in the hip, but we expected a 7.3-10.3% dropout rate based on the results of a similar study in the knee. However, as of July 2018, we had 47 patients that had passed the 2-year follow-up mark, of which 5 patients were no longer in the study (combination of lost to follow-up and proceeding to total hip arthroplasty), and another 11 had yet to complete their 2-year surveys even with multiple attempts to contact them and encourage them to do so. With a yield of 31 patients out of 47, or 65.95%, we increased our sample size to 122.

Therefore, we estimate needing 122 subjects to achieve 70 study completers, in the appropriate proportion of 35 subjects per treatment arm. We enroll until reaching at least 35 subjects in each group.

The results of the MeTeOR trial in the knee show that we can expect a higher drop-out rate in the surgical group. As such, this cohort may be our limiting factor.^{40, 43, 61, 62}

Specific Aim 2. Hypotheses 2.1-2.3: *To evaluate the significance of arthritic burden on short term outcomes following arthroscopic labral repair.*

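### The effect-size rule for judging a significant between-arm mHHS difference does not work, whether the formula is taken as printed or read as a standardised difference

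*Combined protocol and SAP*

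**What the plan says.** Section V, Hypothesis 1.1-1.4, compares mHHS at 12 months with baseline within each arm by paired t-test, and between arms by independent t-test. An ES then follows, but only on a condition: "If a statistically significant difference is detected during these analyses, we will calculate the effect size (ES". Its stated purpose is to show how much the result means beyond its p-value. The printed formula divides the surgical-arm mean by the conservative-arm mean, and divides that quotient by the conservative-arm SD. The scale is: "an ES <0.1 is trivial, ES of 0.1-0.3 is minimal, ES of 0.3-0.5, is moderate, and ES >0.5 is large".

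The Power Analysis for Specific Aim 1 sizes the between-arm comparison on "a 10 point or greater difference on the mHHS as significant", with "a single-tail independent t-test to evaluate the difference between means with 80% power and a 5% significance level". It concludes that "35 subjects are needed to demonstrate a statistically significant difference", and later makes clear that this is per arm: "in the appropriate proportion of 35 subjects per treatment arm". Enrolment is set by the statement that "we estimate needing 122 subjects to achieve 70 study completers". The SD behind the calculation is not given; the source is described only as "Using the data from our retrospective review of outcomes following labral repair". Nothing connects the ES labels to the 10 points.

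**The concern.** A grading applied after significance is useful only if it can separate important results from significant but unimportant ones. Here it cannot do so for the comparison behind Hypothesis 1.3, the superiority of surgery plus PT over PT alone. The printed formula does not measure a difference between arms. The formula presumably meant makes the two unfavourable labels unreachable at the planned size, and it may set the boundary of 'large' below the difference the trial was designed to detect.

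At stake is how the main result is described. A surgical advantage short of 10 points could be reported as 'large'; under the printed formula, a difference that meets 10 points would be reported as 'trivial'. After a non-significant result no ES is planned, although section I (Implications) allows that PT may prove equal or better. In that case the size of the difference and its uncertainty are what a reader most needs.

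**Working it through.** **Inputs.** From the Power Analysis: 10-point difference, one-sided 5%, 80% power, 35 completers per arm. Enrolment is 122; at the observed yield of 31/47, 122 × 31/47 = 80.5, or about 40 per arm. Full completion would give 122/2 = 61 per arm. The analysis section does not state the sidedness of the t-tests, so both are shown.

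**1. The plan's own figure.** Without an SD, 35 per arm cannot be checked independently. Solving the two-sample t-test power equation for the SD that makes 35 per arm give 80% power at 10 points:
- one-sided: standardised difference 0.600, SD = 10/0.600 = 16.7 (16.66 before rounding);
- two-sided: standardised difference 0.679, SD = 10/0.679 = 14.7 (14.72 before rounding).

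These values reproduce 35 by construction. They are inferences, not figures in the plan.

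**2. Formula as printed.** ES = (surgical mean / conservative mean) / conservative SD.
- 80 against 70, SD 16.7: (80/70)/16.7 = 1.143/16.7 = 0.068.
- 80 against 70, SD 14.7: 1.143/14.7 = 0.078.
- 100 against 50, SD 16.7: 2/16.7 = 0.12.

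The 10-point difference is 'trivial', and even a 50-point difference is only 'minimal'. To reach 'moderate' at SD 16.7, the ratio of means would have to be 0.3 × 16.7 = 5.0.

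**3. Formula read as (surgical mean − conservative mean) / SD.** With about equal SDs, the smallest significant ES is t_crit × √(2/n), with 2n − 2 degrees of freedom. No SD is needed.

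| Per arm | One-sided | Two-sided |
|---|---|---|
| 35 | 1.668 × 0.239 = 0.399 | 1.995 × 0.239 = 0.477 |
| 40 | 1.665 × 0.224 = 0.372 | 1.991 × 0.224 = 0.445 |
| 61 | 1.658 × 0.181 = 0.300 | 1.980 × 0.181 = 0.359 |

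At every size up to full completion, a significant between-arm ES is at least 0.30, so 'trivial' and 'minimal' cannot be returned. Unequal SDs hardly change this. Dividing by the conservative-arm SD at 35 per arm, a significant ES can fall below 0.3 only if the surgical SD is under about 0.34 of the conservative SD (one-sided), and never two-sided.

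**4. Where 'large' starts in points.** This is 0.5 × SD.
- SD 16.66: 8.3 points.
- SD 14.72: 7.4 points.
- SD 20: 10 points.

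At either implied SD, 'large' begins below 10 points. At SD 20 or more it begins at or above 10 and the conflict is gone. An SD of 20 would need about 50 per arm for 80% power one-sided, so it does not fit the planned 35, but it could still be observed.

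**5. Within-arm paired tests.** The smallest significant mean change over the SD of change is t_crit/√n. At n = 35 this is 1.691/5.916 = 0.286 one-sided and 2.032/5.916 = 0.344 two-sided. In baseline-SD units, with an assumed correlation of 0.7, multiply by √(2 × 0.3) = 0.775, giving 0.22 and 0.27. A significant 'minimal' result is therefore possible there.

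**The case against.** The strongest objection is that the point about unreachable labels concerns a formula the plan does not print. Taken literally, the formula labels almost everything 'trivial', the opposite problem. That is correct, so the formula must be corrected first; whether a minus sign was intended cannot be told from the text. But the grading is uninformative on either reading.

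A reader might infer that every significant result in the plan would be called 'moderate' or 'large'. The documents do not support that. The analyses that can trigger an ES include the paired tests against baseline, where significance below 0.3 is possible and for which no ES formula is given.

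A reader might also infer that the plan's own figures prove 'large' lies below its threshold. They do not. The SD is inferred, the planning data come from labral-repair patients, and the ES would use the observed conservative-arm SD. The 10 points are an input to the power calculation and are not declared a threshold for interpreting the observed result. They are, however, the only between-arm mHHS benchmark the plan offers.

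Nor is it right that the labels carry no information: 'moderate' and 'large' can still be told apart under the difference reading. And a non-significant result would not be left without any figures, since the arm means are compared regardless; what is missing is a planned ES or a stated interval.

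**Conclusion.** The concern holds for the between-arm mHHS comparison. As printed, the ES labels practically every result 'trivial'. Read as a standardised difference with about equal SDs, it can return only 'moderate' or 'large' after significance, with a floor of about 0.37 to 0.48 at 35 to 40 per arm. That floor depends on sample size and significance level alone, and is secure.

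The second part is conditional. 'Large' starts at about 8.3 points (SD 16.7, one-sided design) or 7.4 points (SD 14.7, two-sided design) only if the observed conservative-arm SD resembles the one implied by 35 per arm. The range of differences affected is then narrow: roughly 8.3 to 10 points, or 7.4 to 10. The test and the sample size are untouched; the interpretation of the main result is not. It should be corrected, with medium confidence because the SD is not documented.

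**What to change.** 1. Correct the ES to (surgical mean − conservative mean) / SD, and state which SD is used.
2. Report the between-arm mHHS difference in points with its 95% CI, whether or not the test is significant.
3. Discuss that difference and interval against the 10-point design difference, and stop using the four labels to decide meaningfulness.

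A formal three-way rule (meaningful if the lower limit is at least 10, not meaningful if the upper limit is below 10, otherwise uncertain) is not recommended. At 35 per arm and SD 16.7 the 95% CI half-width is 1.995 × 16.7 × √(2/35) = 8.0 points. An observed difference of about 18 would be needed for the first verdict and below about 2 for the second. When the true difference is 10, the interval covers 10, and the rule returns 'uncertain', about 95% of the time.

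The cost is a change of wording in section V, with no new data or subjects. The downside is that the description of a modest positive result becomes less favourable.

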Determining which patients, using age and arthritic burden as predictors, can benefit from labral repair is paramount for several reasons. Showing arthroscopic repair is of little or no benefit to a specific cohort can reduce the number of unnecessary surgeries performed, increase the use of conservative therapy (if validated) and reduce the interval between diagnosis and total hip replacement. Additionally, proving a benefit exists from arthroscopic repair in a certain subset of the population will substantiate the need for developing a treatment algorithm in older patients presenting with labral tears and some degree of pre-existing arthritis. Furthermore, conservative physical therapy may prove to be of equal or greater benefit than arthroscopic repair in select patients. If true, this study will be a landmark for providing the evidence needed to recommend conservative treatment as an efficacious alternative in addition to providing a foundation for future research on this topic.

II. SPECIFIC AIMS:

Specific Aim 1: To evaluate if physical therapy alone or arthroscopic labral repair and physical therapy is of greater benefit to patients presenting at age 40 with tears of the acetabular labrum.

Hypothesis 1.1: Physical therapy will result in a significant difference in mHHS scoring at 12 months when compared to baseline.

Hypothesis 1.2: Arthroscopic labral repair will result in a significant difference in mHHS scoring at 12 months when compared to baseline.

Hypothesis 1.3: Arthroscopic labral repair and physical therapy will be superior to physical therapy alone in improving function and alleviating symptoms at 12 months when compared to baseline, as judged by the mHHS.

Hypothesis 1.4: Hypotheses 1.1-1.3 will hold true at 24 months and beyond.

Hypothesis 1.5: Functional outcome scores collected at the completion of PT will not significantly differ from those collected at 12 and 24 months and beyond in the same group.

Specific Aim 2: To evaluate the effect of arthritic burden on short term outcomes following arthroscopic labral repair.

Hypothesis 2.1: In the surgical treatment group, subjects with arthroscopically proven severe osteoarthritis (Outerbridge grade 4) will do more poorly on validated outcome measures, specifically the mHHS, after arthroscopy than subjects with less severe osteoarthritis (Outerbridge grade ≤ 3).

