We plan to track the effects of OA on outcomes through identification and localization of OA at the time of arthroscopy using a mapping technique (see diagram). After complete visualization of the intra-articular space, as is standard practice in hip arthroscopy, classification of any existing osteoarthritis will be done according to the Outerbridge grading scale. Using this system, we are able to categorically group subjects based on location and severity of disease. If multiple lesions are present, subjects will be characterized by the most severe grade. Furthermore, based on the data gathered through meeting hypotheses 1.1-1.4, we will subdivide primary outcome scores into four categories.⁶⁰ Category I, excellent outcomes (mHHS ≥ 90); Category II, good outcomes (mHHS ≥ 80); Category III, fair outcomes (mHHS ≥ 70), and Category IV, poor outcomes (mHHS < 70). The likelihood of outcomes based on Outerbridge grading and outcome category will be determined through odds ratios. Analysis will be carried out using Chi-squared tests. Significance is set at $P < 0.05$. Linear regression analysis will be performed to detect if any relationship exists between the severity of osteoarthritis and short-term outcome scoring.

Hypothesis 3.1:

This is an exploratory hypothesis whose assessment will no influence the other data sets. Prior work by other groups has demonstrated that evaluation of arthritic burden by conventional measures (Kellgren-Lawrence and Tonnis grading) are not indicative of the severity of arthritis found at the time of arthroscopy.⁵⁸ We will explore this phenomenon in our own cohort of subjects, specifically those in the surgical group and report our findings. We will correlate our findings for significance.

Power Analysis:

Specific Aim 1, Hypotheses 1.1-1.4: *To evaluate if physical therapy alone or arthroscopic labral repair and physical therapy is of greater benefit to patients presenting at age 40 with tears of the acetabular labrum.*

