Hypothesis 2.1 was powered on the basis of our prior work where 33% of study participants had grade 4 Outerbridge changes the time of arthroscopy. Dividing our cohort into two subgroups: 1) Those with grade 4 changes and 2) Those without. We will need 12 subjects with grade 4 changes in order to perform adequate sub-group analysis.⁶³ Powered to 80% and 5% significance level. Hypothesis 2.2 is another sub-group analysis that will be conducted in a similar fashion to that of hypothesis 2.1. However, the two groups will be categorized into: 1) cartilage defects at or near the chondro-labral junction and 2) cartilage defects not at or near the chondro-labral junction. We cannot control the heterogeneity of the subjects enrolled, but based on this analysis we expect to meet our target enrollment. Hypothesis 2.3 will be analyzed via linear regression and is appropriately powered.

Specific Aim 3 is exploratory. Since we are recruiting subjects for the main purposes of determining outcomes, we recognize that we may be underpowered for the definitive analyses of our radiographic correlation hypotheses. Nevertheless, we anticipate that we will enroll sufficient numbers of subjects to draw an association or at the very least, trend patient outcomes with degree of joint space narrowing, Kellgren-Lawrence grading, and Tonnis grading. There should also be sufficient numbers to preliminarily assess any correlations between pre-operative Kellgren-Lawrence and Tonnis grades with the Outerbridge classification at the time of arthroscopy.

VI. RISKS & DISCOMFORTS

Conservative Treatment: Subjects can expect the routine discomfort associated with any therapeutic procedure. Complications may include muscle soreness, pain, and increased edema or muscle fatigue.

Operative treatment: Since surgery is not considered a research procedure (only the randomization into the surgery group is considered a research procedure, as explained above) surgical risks are explained in the surgical consent process.

In the rehabilitation period, patients will be subject to the same potentials discomforts as those subjects in the conservative treatment group as the physical therapy protocols for both groups are identical. In both treatment groups every effort will be made to minimize the risk of adverse events and patient discomfort.

VII. POTENTIAL BENEFITS:

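### Hypothesis 2.1 should be decided by a grade 4 versus grade ≤3 contrast on continuous mHHS; the planned four-band Chi-squared loses power, and the plan does not say whether it or the regression decides

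*Combined protocol and SAP*

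**What the plan says.** Section II (Specific Aims) limits Hypothesis 2.1 to the surgical treatment group and states a two-group contrast against grade ≤3: "subjects with arthroscopically proven severe osteoarthritis (Outerbridge grade 4) will do more poorly on validated outcome measures, specifically the mHHS". The Power Analysis for Specific Aim 2 uses the same split, "Dividing our cohort into two subgroups: 1) Those with grade 4 changes and 2) Those without", and adds "We will need 12 subjects with grade 4 changes in order to perform adequate sub-group analysis", claiming 80% power at the 5% level. It gives no effect size, SD, sidedness or test for that claim.

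Section V, under Hypotheses 2.1 to 2.3, describes the analysis differently. On the outcome: "we will subdivide primary outcome scores into four categories", with cut-points at 90, 80 and 70. On the measure: "The likelihood of outcomes based on Outerbridge grading and outcome category will be determined through odds ratios". On the test: "Analysis will be carried out using Chi-squared tests". The paragraph closes with a second method: "Linear regression analysis will be performed to detect if any relationship exists between the severity of osteoarthritis and short-term outcome scoring".

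Four things are left open: how many grade rows the table has, how severity is coded in the regression, what is done if counts are small, and whether Chi-squared or regression settles the hypothesis.

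**The concern.** The hypothesis concerns a difference in score between two groups. Chi-squared on four bands asks a looser question: whether the band distribution differs in any way. It ignores the order of the bands and all variation within them. In a group of about 35, with about 12 in the smaller subgroup, that is expensive, and the table is too sparse for the usual count rule.

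Aim 2 is not labelled exploratory, and Section I makes arthritic burden central to deciding who benefits from repair. A non-significant Chi-squared could be read as showing that grade 4 disease does not matter when the test had little chance of detecting it. With two methods and no ranking, the result to emphasise could also be chosen after the data are seen.

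**Working it through.** **Inputs from the documents.** At least 35 completers per arm; 122 enrolled in total; 33% at grade 4; 12 grade 4 subjects required; four mHHS bands; score maximum 100.1; a 10-point mHHS difference treated as meaningful in Aim 1 (one-sided t-test, 80% power, 5% level).

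**The plan's own figure.** 0.33 × 35 = 11.55, which rounds up to 12. So the 12 equals the expected number of grade 4 subjects in a 35-subject arm. The 80% power attached to it cannot be reproduced, because its ingredients are not given.

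**Assumptions.** The documents give no SD. Solving Aim 1's 35 per arm gives d = 0.600, so SD = 10 / 0.600 ≈ 16.7. I used SDs of 14 to 20, a grade ≤3 mean of 75 to 90, normal scores capped at 100.1, 12 versus 23 subjects and two-sided tests. For tables with all grades, I assumed grades 0 to 4 with the 23 spread evenly over 0 to 3.

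**Counts.** The expected counts in the grade 4 row sum to 12. Three cells at 5 or more would need 15, so at most two of the four can reach 5. With all four bands occupied, at least 2 of 8 cells (25%) therefore fall below 5, against the usual limit of 20%. In simulation the average was about 5.3 of 8, and every table breached the limit. With all five grades as rows, the mean expected count is 35 / 20 = 1.75.

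**Type I error.** With no true difference, the 2×4 test rejected about 3-5% of the time across separate simulations, and the 5×4 test 4.8%. Neither is inflated.

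**Power at SD 16.7, 12 versus 23, only grade 4 differing** (ranges over grade ≤3 means of 75 to 90):

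| True deficit | 2×4 Chi-squared | Continuous grade 4 vs ≤3 |
|---|---|---|
| 10 points | 14-24% | 37-39% |
| 15 points | 28-44% | 67-70% |
| 17 points | 38-58% | 80-82% |

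Relative loss = 1 − (banded power / continuous power). Examples:
- 17 points, mean 75: 1 − 0.381/0.809 = 53%.
- 17 points, mean 90: 1 − 0.583/0.807 = 28%.
- SD 14, 10 points, mean 75: 1 − 0.178/0.490 = 64%.

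Over all scenarios the 2×4 loss was 23-64%. For the 5×4 table it was 64-82% if only grade 4 differs and 39-60% if the effect is linear in grade.

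**Regression on ordinal grade.** If only grade 4 differs, regressing on the grade number gives about 60% power at 17 points, against 80-82% for the two-group contrast. If the effect is truly linear in grade, the ordering reverses: 52% against 37% at 10 points.

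**What the continuous contrast can achieve.** For 10 points, the noncentrality is (10/16.66) × √(12 × 23 / 35) = 0.600 × 2.808 ≈ 1.69, which gives 37% power two-sided (50% one-sided). Power of 80% needs d = 1.03 two-sided, that is 1.03 × 16.66 ≈ 17 points.

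**The case against.** A reader might make three stronger inferences, and none is supported.

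- **That the Chi-squared P value is invalid.** The count rule is a rule of thumb. It is breached, but the simulated false-positive rate stays at or below about 5%.
- **That half or more of the power is always lost.** This is generally true only if all grades are tabulated, and neither Section II nor the Power Analysis defines Hypothesis 2.1 that way. For the two-group table the loss is below half in most scenarios.
- **That the continuous score is thrown away.** The same paragraph plans a regression on outcome score. The gap is that this regression is not named as decisive and that severity is not coded as grade 4 versus the rest.

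Two further points against the concern have weight. First, 35 is a floor, and the attrition behind 122 was observed at two years. If allocation is 1:1, up to 122 / 2 = 61 surgical subjects could contribute at 12 months, about 0.33 × 61 ≈ 20 at grade 4. At 20 versus 41, the 2×4 loss falls to about 5-47%, and at SD 16.7 and a grade ≤3 mean of 80 its power is 34% at 10 points and 64% at 15. Even so, 90-99% of tables still breach the count rule. Second, at 10 points and 35 subjects the continuous analysis would also usually miss the effect. That part is a sample-size limit, which no choice of test removes.

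**Conclusion.** The concern stands as a choice of a weaker method together with an unranked pair of analyses. It is not a finding that the test is invalid. At the planned minimum, the four-band Chi-squared loses roughly 25-65% of the power of a continuous comparison for the contrast that Hypothesis 2.1 defines, and about 40-80% if every grade is a row. The planned regression does not fully close the gap if severity is entered as ordinal grade and only grade 4 differs.

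The breach of the count rule follows from the plan's own 12 subjects and four occupied bands. The power figures rest on the assumed SD, means and spread of lower grades, and they shrink if more than 35 surgical subjects contribute data.

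**What to change.** In Section V, name one decisive analysis for Hypothesis 2.1: linear regression of continuous 12-month mHHS on grade 4 versus grade ≤3 in the surgical group, adjusted for baseline mHHS, with the estimated difference and its confidence interval reported. Show the four-band table and the odds ratios descriptively. A regression on ordinal grade can be kept as a labelled secondary analysis.

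Replacing Chi-squared with Fisher's exact test on mHHS below 70 versus 70 or above would not recover the power. At a mean of 80 and SD 16.7 it gave 19% at 10 points and 41% at 15, against 18% and 35% for the 2×4 Chi-squared.

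In the Power Analysis, state the difference that 12 grade 4 subjects can detect (about 17 points two-sided at SD 16.7, before baseline adjustment), so that a null result is not over-read. The gain from baseline adjustment was not quantified, because the documents give no baseline correlation.

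The cost is a change of wording. All the data are already planned for collection, and there is no material downside.
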